6.12.2 Secondary Safety Endpoints

The following secondary safety endpoints will be assessed:

- The time from randomization to the first occurrence of any Antiplatelet Trialists' Collaborative (APTC) event (CV Death, Non-fatal MI, and Non-fatal Stroke).
- The time from randomization to the occurrence of each individual event in the pre-defined MACE composite.

Survival analysis using the CPH model will be performed on the time to the first occurrence of any APTC event and on the time to occurrence of each individual event in the pre-defined MACE composite. Parameter estimates and 2-sided 95% CIs for the hazard ratio will be computed. A graphical display indicating the point and 95% CI estimates of the hazard ratios for the primary MACE components will also be presented.

To identify risk factors for the time to first occurrence of APTC event, an exploratory analysis will also be performed using multivariate CPH modeling. The multivariate model will include treatment group and the following covariates jointly in the model with baseline renal function as the stratification factor: age, gender, BMI, NSAIDs use, low-dose aspirin use, smoking history, baseline sUA, and history of diabetes, hypertension, non-fatal MI, or non-fatal stroke. No interaction terms will be introduced in the multivariate model. The backward elimination technique with a significance level to stay (SLS) in the model of SLS = 0.05 will be implemented for variable selection while always retaining treatment group and baseline renal function as stratification factor in the model.

In addition, Kaplan-Meier plots for the time to first occurrence of APTC event and the time to first occurrence of each individual event in the pre-defined MACE will be presented by treatment group.

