All subjects will return at Week 2 for measurement of sUA and all subjects will return for a Week 4 and Month 3 visit. If the Week 2 sUA level is <6.0 mg/dL, the subject will be dispensed study medication at Week 4, and the next visit will occur at Month 3. If the Week 2 sUA level is ≥ 6.0 mg/dL, the subject will be dispensed study medication at Week 4, and the next visit will occur at Week 6.

For the subset of subjects who have a Week 6 visit, if the Week 6 sUA level is <6.0 mg/dL, the subject will be dispensed study medication at Week 8, and the next visit will occur at Month 3. If the Week 6 sUA level is ≥ 6.0 mg/dL, the subject will be dispensed study medication at Week 8 and the next visit will occur at Week 10.

For the subset of subjects who have a Week 10 visit, the subject will be dispensed study medication at the Month 3 visit. After the Month 3 visit, no further dose adjustments will be made. All subjects will have Month 3 and Month 6 visits.

Following the Month 6 visit, all subjects will have visits every 6 months for the duration of the study. In addition, subjects with moderate renal impairment (eCLcr <60 mL/min) and/or subjects who are elderly (≥ 65 years of age) will have visits at Month 9 and Month 15 to monitor liver function tests. Subjects who are withdrawn from study medication treatment but have not withdrawn consent will be followed via phone calls every 2 months until the end of the study or until the subject experiences a CV event that is positively adjudicated as a MACE.

A Data Monitoring Committee (DMC) will periodically review results obtained in the study, including results at 3 planned interim analyses. They will monitor the progress and the on-going safety of subjects enrolled into the study. An Independent CV Endpoints Committee will be established to prospectively review all suspected CV events using blinded data. A periodic review of all serious adverse events and specific CV adverse event terms will be performed by the Chair of the CV Endpoints Committee. The Chair, not the sponsor, will designate cases for comprehensive review by the CV Endpoints Committee. All investigational sites will be required to collect relevant clinical information required for adjudication of all deaths and potential CV serious adverse events (SAE).

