5.0 DETERMINATION OF SAMPLE SIZE

A total of 7500 subjects (3750 per treatment group) are planned to be enrolled in this study. The sample size will provide at least 90% power to meet a non-inferiority margin of 1.3 for the hazard ratio (febuxostat relative to allopurinol) of the primary endpoint. The sample size calculation assumed a true hazard ratio of 1.0 at a 1-sided 2.5% significance level with 3 interim analyses at approximately 25%, 50% and 75% of the events based on critical values obtained using the Lan-DeMets - O'Brien-Fleming alpha spending function.

For the determination of non-inferiority between the febuxostat treatment group and the allopurinol treatment group, the sample size calculation further assumed:

- Constant proportional hazards and exponential survival curves,
- Annual adjudicated MACE composite rate of 2.8%,
- Maximum length of participation of 5 years,
- Accrual time of 2.5 years, and
- Annual drop-out rate of 10%.

This study is designed to have a maximum of 624 MACE.

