6.12 Safety Analysis

Safety will be assessed by evaluating the incidence of adverse events including cardiovascular adverse events such as predefined MACE composite, and evaluating ECGs; laboratory tests and vital signs. A CV Endpoints Committee blinded to treatment assignment will adjudicate potential cardiovascular adverse events and each death to determine if it meets MACE criteria. The procedures and rules of adjudication of these events by the CV Endpoints Committee is described in a separate charter.

For the primary, secondary, and additional safety endpoints, time to event will be the time from the date of randomization or the date of last dose of study medication to the date of first occurrence of any event in the respective endpoint. If a subject reports an event for a given safety endpoint after treatment discontinuation, the reported event will be counted toward the treatment to which they were randomized. Subjects who are lost to follow-up during the study or who do not exhibit an episode of an event for the specific safety endpoint throughout the study will be censored at the day of last contact.

All safety endpoints will be analyzed using the Full Analysis Set (FAS). The FAS will consist of all subjects who were randomized and received at least one dose of double-blind study medication. Non-inferiority will be assessed only for the primary safety endpoint.

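### Kaplan-Meier curves for single MACE components, with other deaths censored, modestly overstate absolute component risk; cumulative incidence curves would show it correctly

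*SAP*

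**What the plan says.** Section 6.12.2 of the SAP lists as a secondary endpoint "The time from randomization to the occurrence of each individual event in the pre-defined MACE composite". The components are CV death, non-fatal MI, non-fatal stroke, and unstable angina with urgent coronary revascularization. Each gets a Cox model ("Parameter estimates and 2-sided 95% CIs for the hazard ratio will be computed") and a Kaplan-Meier plot: the plots for "the time to first occurrence of each individual event in the pre-defined MACE will be presented by treatment group".

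The censoring rule is in section 6.12 and covers the primary, secondary and additional safety endpoints. For event-free subjects the rule reads: "do not exhibit an episode of an event for the specific safety endpoint throughout the study will be censored at the day of last contact". Death from a cause outside the endpoint is not treated separately.

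Section 3.2 adds that subjects withdrawn from study drug are followed to the end of the study or "until the subject experiences a CV event that is positively adjudicated as a MACE". Section 6.6 likewise sets last contact at the event date for a MACE after treatment discontinuation.

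The SAP plans no cumulative incidence function or other competing-risk method.

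**The concern.** A subject who has died cannot later have a non-fatal MI, a non-fatal stroke or an urgent revascularization, and a subject who has died of a non-CV cause cannot later die of a CV cause. The Kaplan-Meier estimator handles such a subject like one whose follow-up merely stopped. It passes the unobserved risk on to those still under observation. One minus Kaplan-Meier then estimates the risk in a hypothetical setting without other deaths, not the proportion of subjects who have the event.

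At stake is how readers take the curves. For the three non-fatal components, no other planned display shows absolute risk over the whole of follow-up. The component incidence rates in section 6.12.3 count only events up to 30 days after the last dose. A reader who wants the long-term risk of MI or stroke by arm would take it from these plots.

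**Working it through.** **The plan's own figure.** The SAP states no component incidence, so there is none to reproduce. Its event target can be reproduced, and this confirms the constant-hazard model used below.

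- Fixed design, margin 1.3, one-sided 2.5%, 90% power, true hazard ratio 1.0: 4 × (1.960 + 1.282)² / (ln 1.3)² = 611 events.
- With the boundaries in Table 6.c, 622 events are needed, and power at 624 events is 90.1%.
- Section 5.0 assumes "Annual adjudicated MACE composite rate of 2.8"%, "Accrual time of 2.5 years", "Maximum length of participation of 5 years" and 10% annual drop-out. With 7500 subjects and the study ending at 5 years, let λ = 0.028 and h = 0.028 + 0.10 = 0.128. Expected events are 7500 × (λ/h) × [1 − (e^(−2.5h) − e^(−5h)) / (2.5h)] = 621. Converting the annual rates to hazards gives 624.

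**Kaplan-Meier against cumulative incidence.** Let l1 be the component hazard, l2 the competing-death hazard and T the time in years.

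- Value that the Kaplan-Meier plot approaches: 1 − e^(−l1·T)
- True cumulative incidence (the Aalen-Johansen limit): l1/(l1 + l2) × [1 − e^(−(l1 + l2)·T)]

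Both hazards are assumptions: l1 from 0.7 to 1.5% per year, l2 from 1.5 to 3.5% per year. The horizons are 5 years (planned maximum participation) and 7 years (Table 6.a runs to Month 84).

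Worked example, l1 = 0.010, l2 = 0.025, T = 7:

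- Kaplan-Meier: 1 − e^(−0.07) = 6.76%
- Cumulative incidence: (0.010/0.035) × (1 − e^(−0.245)) = 0.2857 × 0.2173 = 6.21%
- Excess: 0.55 percentage points, or 8.9% relative

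| l1 per year | l2 per year | T | 1 − KM | Cumulative incidence | Relative excess |
|---|---|---|---|---|---|
| 1.5% | 1.5% | 5 | 7.23% | 6.97% | 3.7% |
| 0.7% | 3.5% | 5 | 3.44% | 3.16% | 8.9% |
| 1.5% | 1.5% | 7 | 9.97% | 9.47% | 5.2% |
| 0.7% | 3.5% | 7 | 4.78% | 4.25% | 12.6% |

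These rows are the extremes of the relative excess. It depends almost entirely on l2 and T and hardly on l1.

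**CV death.** Only non-CV death competes. If that is 0.5 to 1.5% per year (assumption), the relative excess at 7 years is 1.7 to 5.3%.

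**Arm contrast.** Take the same component hazard of 1.0% per year in both arms and competing death of 2.4% against 2.0% per year. Both Kaplan-Meier curves reach 6.76% at 7 years. The cumulative incidences are 6.23% and 6.31%, a difference of 0.08 percentage points.

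**Follow-up that ends at another component.** For subjects off drug, a first adjudicated MACE of a different type also ends observation. As an illustration, let the rest of the 2.8% composite compete with a component at 1.0% per year, so the competing hazard is 1.8% per year with no non-CV death added. At 7 years Kaplan-Meier gives 6.76%, while the cumulative incidence of that component as first event is 6.36%. This bounds the case where every subject's observation stops at the first MACE; section 3.2 says so only for those off drug.

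**The case against.** The strongest reply is that the SAP never says one minus Kaplan-Meier will be reported as the proportion with the event, and it plans no component risk at a fixed year. Section 6.12.1 uses Kaplan-Meier curves of the primary endpoint partly to inspect proportional hazards. Censoring other deaths also matches the cause-specific Cox model planned for the components. On that view the choice is one of display. This stands as far as inference goes: non-inferiority is tested only on the primary endpoint, and the component hazard ratios do not depend on the plots. It does not remove the problem for a reader who takes absolute risk from the curves.

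A second reply is that the size is assumed. That stands too. The upper competing-death rate of 3.5% per year exceeds the whole planned MACE rate, and the 13% figure needs 7 years against a planned maximum of 5. The excess is also not large beside sampling error: with 3750 per arm and no censoring, the 95% half-width around 4.9% is about 0.7 percentage points.

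A reader might infer more, namely that the overstatement distorts the comparison of arms on the very question for which the trial was continued. The document does not support this. Section 6.13 says continuation was for all-cause and CV mortality. All-cause death from randomization has no competing event. Section 6.12.3 also reports deaths overall and by CV and non-CV cause with exact binomial intervals, which do not use Kaplan-Meier. Of the four component curves only CV death bears on that question, and its excess is the smallest. A difference of 0.08 percentage points between arms is negligible. Cumulative incidence also makes the arm with more deaths look slightly better on the component, so it should not be the only comparative measure.

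**Conclusion.** The point holds as a modest improvement to a descriptive display. Sections 6.12 and 6.12.2 together produce component curves that overstate absolute risk whenever competing deaths occur. The direction is certain. The size depends on constant hazards and on rates that the SAP does not give. Under the assumed ranges the excess is about 4 to 9% relative at 5 years and 5 to 13% at 7 years, at most about 1.1 percentage points. The cause-specific Cox hazard ratios, the 624-event design and the non-inferiority conclusion are untouched.

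**What to change.** In section 6.12.2, present Aalen-Johansen cumulative incidence curves by arm for each component as the absolute-risk display. Define the competing event as follows:

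- For non-fatal MI, non-fatal stroke, and unstable angina with urgent revascularization: any death not counted as the component.
- For CV death: non-CV death.
- Where observation ends at a first adjudicated MACE of another type: treat that event as competing too, or analyse first events only, and say which.

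Keep the Cox hazard ratios and label them cause-specific. Kaplan-Meier plots may stay for checking proportional hazards.

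The cost is one additional plot method, and the curves will sit slightly lower. No new data are needed: each death is already adjudicated, and mortality is already split into CV and non-CV cause.

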6.12.3 Other Safety Endpoints

The following additional safety endpoints will also be assessed:

- The time from randomization to the first occurrence of any event in the pre-defined MACE composite plus any of the following events:

- Urgent Cerebral revascularization [non-elective].
- Hospitalized congestive heart failure (CHF).
- Arrhythmias not associated with ischemia.
- Venous and peripheral arterial thromboembolic events; eg, Deep Vein Thrombosis (DVT) and Pulmonary Embolism (PE).
- Transient Ischemic Attack (TIA).
- The time from randomization to the occurrence of all-cause death,
- The time from randomization to the occurrence of all-cause death during treatment (from randomization to last dose of study medication),
- The time from last dose of study medication to the occurrence of all-cause death,

Survival analysis using the CPH model will be performed for these additional endpoints. Parameter estimates and a 2-sided 95% CI for the hazard ratio will be computed.

Kaplan-Meier plots will also be presented by treatment group.

The following other additional safety analyses will also be performed:

- The number of subjects with first occurrence of predefined MACE that occur no more than 30 days after a subject's last dose of study drug and the associated incidence rate by 100 patient-years of exposure along with 95% confidence intervals will be summarized by treatment group. The 95% CIs will be calculated based on the Poisson distribution. For a given treatment total patient-years (PY) of exposure will be calculated by summing across all subjects the total number of days on the treatment and dividing by 365.

The same analysis will be performed for each component of the MACE composite.

- Mortality analyses for the overall and by CV and Non-CV cause. The total number deaths and the death rate with 95% CI will be presented. The 95% CIs for the death rate will be calculated based on the Binomial distribution using exact method.
- The number and percentage of subjects with first occurrence of a pre-defined MACE composite will be presented by number of days in the study.
- List of CV risk factors for subjects with a predefined MACE composite comprising diabetes, hypertension, hyperlipidemia, obesity, and smoking will be provided by treatment group. Listings include subject number, age, gender, baseline renal function, primary MACE component, disposition, primary reason for discontinuation if disposition is early term, and CV risk factors.

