At the DMC meeting on ^{PPD} [REDACTED], the 75% interim analysis results based on 468 adjudicated MACE for the primary MACE endpoint to assess cardiovascular safety was reviewed by the DMC. At the DMC meeting on ^{PPD} [REDACTED], the DMC informed Takeda that the non-inferiority criterion for the primary endpoint was met at the 75% interim analysis conducted in ^{PPD} [REDACTED]. According to the study design, the study should have been stopped and the non-inferiority of febuxostat relative to allopurinol with regard to cardiovascular risk should have been declared. However the DMC recommendation was to continue the trial without modification until the maximum 624 unique events were achieved to further assess all cause mortality (which was not a protocol specified endpoint) and CV mortality (which is specified only as a component of the MACE endpoint). Takeda agreed to follow the DMC recommendation and continue the study.

Based on the group sequential design, the 75% interim analysis will be the primary analysis for the primary MACE endpoint for the purpose of statistical inference. The continuation of the study to protocol-specified maximum events (624 unique MACE) is for the assessment of all cause mortality and CV mortality. The analyses of all cause mortality and CV mortality with and without death events after discontinuation of treatments will be added to the end of study analysis. An updated sensitivity analysis for the primary MACE endpoint based on 624 unique MACE will also be conducted to provide additional supportive evidence for the primary endpoint.

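### Death during treatment ends at the last dose, but the SAP's only censoring date for it is last contact, so off-drug subjects stay in the risk set

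*SAP*

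**What the plan says.** **The endpoint.** SAP 4.3 and 6.12.3 list, as an additional safety endpoint, "The time from randomization to the occurrence of all-cause death during treatment (from randomization to last dose of study medication"). Its companion starts where it ends: "The time from last dose of study medication to the occurrence of all-cause death". Total all-cause death from randomization is listed as well. All three are to be analysed with a Cox model and Kaplan-Meier plots.

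**The censoring rule.** SAP 6.12 opens its timing paragraph by naming the primary, secondary and additional safety endpoints. For these, "time to event will be the time from the date of randomization or the date of last dose of study medication" to the first event. Subjects lost to follow-up, or without an event "for the specific safety endpoint throughout the study will be censored at the day of last contact". No other censoring date is given, and no exception is made for an endpoint that ends at last dose.

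**Follow-up off drug.** SAP 3.2: "Subjects who are withdrawn from study medication treatment but have not withdrawn consent will be followed via phone calls every 2 months". These calls stop at study end or at an adjudicated MACE.

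**Neighbouring windows.** SAP 6.12.3 also plans a rate for "first occurrence of predefined MACE that occur no more than 30 days after a" subject's last dose, and adds: "The same analysis will be performed for each component of the MACE composite". CV death is one of those components. The MACE sensitivity analysis in 6.12.1 and the TEAE definition in 6.12.4 also run to 30 days. SAP 6.13 adds, for the end of study, analyses of "all cause mortality and CV mortality with and without death events after discontinuation of treatments".

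**The concern.** An event that can occur only on drug needs a risk set made up of people on drug. Under 6.12 as written, a subject who stops drug in year 1 and is phoned until year 4 contributes three further years at risk with no possibility of an event.

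Two things follow. The estimated probability of death during treatment is too low in both arms. And if the arms stop drug at different rates, the arm that stops more carries more of this event-free time and looks safer.

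The split between deaths on and off drug bears on how the mortality result is read, and 6.13 gives all-cause and CV mortality as the reason for continuing to 624 events. The choice of censoring date should therefore be settled in writing before unblinding, not left to whoever programs the table.

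**Working it through.** The SAP gives no figure for death during treatment, so there is none to reproduce on this point. The one design figure, 624 events, does not enter. It does reproduce: with margin 1.3, true hazard ratio 1.0, one-sided 0.025 and the Table 6.c boundaries, 622 events give 90% power, and 624 give 0.901.

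**Inputs**

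| Input | Value | Source |
|---|---|---|
| Follow-up per subject | uniform, 2.5 to 5 years | SAP 5.0 (accrual 2.5 years, maximum participation 5 years) |
| Stopping rate *d* | 0.10 per year as base; 0.05 and 0.20 as range | 0.10 is the drop-out figure in SAP 5.0, which may not equal drug discontinuation; the rest is assumed |
| Death rate *h* | 0.01 to 0.03 per year, same in both arms | assumed |
| Off-drug subjects still followed, *c* | 0.5 or 1.0 | assumed |
| True on-drug hazard ratio | 1.00 | assumed |

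**Model.** At time *t* the share on drug is on = exp(−(h+d)t). The share off drug but still followed is off = c·exp(−ht)·(1 − exp(−dt)). With last-dose censoring the event hazard is *h*. With last-contact censoring it is h·on/(on+off), because the off-drug group sits in the denominator only.

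**Equal stopping, 4-year Kaplan-Meier, h = 0.02, d = 0.10**

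- Last-dose censoring: 1 − exp(−0.02 × 4) = 0.077.
- Last contact, c = 1.0: cumulative hazard = 0.02 × (1 − exp(−0.4))/0.10 = 0.02 × 3.297 = 0.0659; 1 − exp(−0.0659) = 0.064.
- Last contact, c = 0.5: cumulative hazard = 0.02 × (2/0.10) × ln[2/(1 + exp(−0.4))] = 0.02 × 3.603 = 0.0721; 1 − exp(−0.0721) = 0.070.

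For *d* of 0.05 and 0.20 the last-contact values are 0.070-0.073 and 0.054-0.062. The hazard ratio is 1.00 in every equal-stopping case.

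**Unequal stopping, Cox hazard ratio (arm that stops more versus the other).** Each arm's on and off shares are weighted by the proportion still under follow-up (1 up to 2.5 years, then (5 − t)/2.5). The Cox score equation is solved for the log hazard ratio. Results for h = 0.02:

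| Stopping per year | c = 0.5 | c = 1.0 |
|---|---|---|
| 10% v 10% | 1.00 | 1.00 |
| 12% v 10% | 0.980 | 0.965 |
| 15% v 10% | 0.951 | 0.917 |
| 7.5% v 5% | 0.976 | 0.955 |
| 30% v 20% | 0.904 | 0.854 |

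Taking *h* as 0.01 or 0.03 moves these by about 0.001. Hand check for 15% v 10% at c = 1.0: the apparent hazard ratio at time *t* is exp(−0.05t), the mean event time is 1.74 years, and exp(−0.05 × 1.74) = 0.917. A simulation with 4 × 400,000 subjects per scenario gave 0.980, 0.964, 0.952 and 0.916 for the second and third rows.

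**Cost of a 30-day window.** At most 7500 × 30/365 = 616 person-years in both arms together. At 1 to 3% per year that is 6.2 to 18.5 background deaths.

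**The case against.** **The parenthesis already bounds the endpoint.** The strongest reply is that a specific definition overrides a general rule. Section 6.12 also counts events after discontinuation, which cannot apply literally to a during-treatment endpoint, so 6.12 must already give way. A competent programmer may well censor at last dose. That is fair, and it is why one sentence settles the matter. But the parenthesis says which deaths count, not when survivors leave the risk set, and 6.12 names the additional endpoints in its scope.

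**The hazard-ratio shift needs unequal stopping.** This stands. The SAP gives no arm-specific stopping rate, so a reader should not infer that the trial's hazard ratio is biased, only that it could be. The follow-up used here is also the sample-size assumption. SAP 3.2 expects a study of about 9 years, and longer follow-up would enlarge the shift (about 0.94 and 0.90 for 15% v 10% at 2.5 to 7 years).

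**Last-dose censoring is not unbiased in general.** This stands too. It returns 1.00 and 7.7% above only because stopping was modelled as unrelated to death risk. If sicker subjects stop drug, and more so in one arm, it can mislead as well.

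**Stronger readings that the SAP does not support.**

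- A reader might call the zero-day death window and the 30-day MACE windows a contradiction. Each is a stated definition for its own analysis, and 6.12.3 does not label the 30-day rates as on-treatment.
- A reader might say that 6.13 leaves its mortality analyses without a lag. Excluding deaths after discontinuation most naturally means zero days, in line with 6.12.3; a cross-reference would merely confirm it.
- A reader might take the rule in 6.6, which sets last contact to the MACE start date for MACE after discontinuation, as censoring mortality there. The rule sits with the definition of study participation, and no effect on mortality can be sized from the SAP.

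**Conclusion.** The point holds for censoring. As written, the only censoring date in the SAP does not fit death during treatment, and applying it literally gives a wrong estimate.

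The absolute risk is understated even with equal stopping: 6.4-7.0% instead of 7.7% at 4 years, with 2% deaths and 10% stopping per year and half to all off-drug subjects followed. The hazard ratio is wrong only if stopping differs between arms, for example 0.92-0.95 instead of 1.00 at 15% v 10% per year. The death rates, the arm-specific stopping rates and the share followed are assumptions.

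The reach is limited. This is an additional endpoint, total all-cause death from randomization is analysed beside it, and non-inferiority is assessed only for the primary endpoint. The primary MACE analysis, the interim decision and the 624-event design do not change. It is still worth settling before database lock, because mortality is the stated reason for continuing the trial.

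**What to change.** 1. **In 6.12.3, as a stated exception to 6.12:** for death during treatment, censor subjects without the event at the earlier of last dose and the last date known alive. Note that this assumes stopping drug is not related to death risk, and that death from randomization therefore remains the main mortality comparison.
2. **Cheap addition in 6.12.3:** keep the zero-day analysis and run beside it all-cause and CV death through 30 days after last dose, censored at the end of that window or the last date known alive if earlier. This lines up with the 30-day MACE windows in 6.12.1 and 6.12.3.
3. **In 6.13, by the un-blinded team that wrote that text:** state that the analyses without deaths after discontinuation use these same windows and censoring dates.

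The death endpoints in 6.12.3 came in with Amendment 2, so the mismatch between 6.12 and 6.12.3 is reason enough for items 1 and 2, without reference to the sequestered Amendment 3.

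**Cost.** A few sentences, one cross-reference and a few extra model runs on data already collected. The downside of item 2 is some deaths unrelated to drug, at most about 6 to 18 in both arms together at the assumed 1 to 3% per year; the zero-day analysis beside it shows how much they matter.
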